#### Participant Adherence:

Dropping out of treatment is common during interventions for antisocial problems (Kazdin & Wassell, 2000; Kazdin & Wasser, 2000) MST has a far superior record of maintaining cases in treatment when compared with MAU (86% vs 79%). Based on 6 studies the RR is highly significantly favouring MST (RR=.69, 95% CI: 0.49, .98). In the BCT following the careful recruitment procedure outlined above, well over 90% of those recruited for either arm of the trial have been retained for the purposes of data collection. We recognise that participation in the various treatment protocols will have lower adherence than data collection as data collection visits are incentivised for both families and young persons by modest compensation for time and travel. To ensure a comprehensive intent to treat analysis the primary outcomes consist of data recorded formally (e.g. out of home placements) which can be measured even if participants have dropped out of treatment and research appointments. In the current trial we have conservatively assumed a 5% dropout at each measurement point, totalling a 15% attrition overall that would effect analysis of secondary outcomes (see Figure 2).

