The primary outcome will be the proportion of cases assigned to long-term (3 months+) out of home placements in specialist residential provision at 18 months following randomisation including placement into local authority care, incarceration, long-term hospitalisation and residential schooling. Adolescents on the edge of care are often placed in boarding schools or even psychiatric hospitals because of a variety factors that currently prevent or in the past have prevented them coming into care earlier so that alternative solutions are sought (e.g. a family may have successfully resisted a previous attempt by LA to obtain a care order etc.). The Children Plan produced by the Department of Children in November conceptualised all integrated children's services as being universal, targeted or specialist. We expect this trial to give information on how many children from MAU and MST required specialist residential provision either immediately or during follow-up period. The Norwegian study identified the relative risk of out of home placements associated with MST 2 years after randomisation to be .59 (95% CI: .32, 1.06) with almost half (48%) of children in the MAU condition being taken into care. The reduction in end of treatment incarceration estimated on the basis of 3 US studies carries an RR of .34 (95% CI: ..20, .56) at treatment termination and .75 (95% CI: .52, 1.07) at 18 months follow-up. The MAU incarceration rate was about 50%. These figures are hard to apply directly to the UK context where both out of home child welfare placements and incarceration is less likely then in the US (50% in MAU). This makes power calculations challenging but following the recommendations for power calculations of Kreamer and colleagues (Kraemer, Mintz, Noda, Tinklenberg, & Yesavage, 2006) We suggest specifying an apriori clinically significant reduction of around 15% in specialist residential provision to be of clinical significance.

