The research team strongly feels that while the rate of out of home placement is an important primary outcome, it is not in every instance an indication of the failure of the system to provide adequate support to the young person and her/his family. Findings have to be interpreted in the context of other outcomes, including general wellbeing, which may in some cases improve following out of home placement. Thus while out of home placement is a critical indicator (and the only measure that can be collected on the entire sample even if the families are lost to data collection interviews), it cannot be considered to be the final arbiter of effectiveness. Placement into specialist residential provision in our view reflects four types of outcome based on two separate factors; the first is about family functioning and the second concerns decisions about where the young person lives. If, following intervention, the family functions in a way that more adequately meets the young person's needs and the young person continues to reside in the family, this constitutes an unequivocally preferred outcome. If, despite intervention, family functioning remains unchanged and is unable to meet young person's needs and the young person is placed out of the family, this constitutes a failure of the intervention (preservation of the family did not succeed) but it is likely to be the best outcome for the young person under the circumstances. The third possible outcome is that, despite intervention, family functioning is still unable to meet the young person's needs but the young person remains in the family. This is the critical instance where an apparently good outcome (family preservation) in fact reflects a nonpreferred (poor) outcome for the young person. The fourth outcome, perhaps less likely, is that the intervention results in better family functioning after intervention but the young person still placed out of home. This will hopefully be rare but could be an 'effective' intervention with respect to psychological outcomes but not with respect to family preservation. In the light of this argument, while we intend to retain out of home placement as the primary outcome, we intend to interpret the family preservation information in the context of the information collected with the self-report wellbeing instruments. So, instances when there is no out of home placement but home observation data and self-report measures suggest that the young person's situation is markedly sub-optimal, the outcome would be coded as a treatment failure as would the secondcategory of outcome listed above.

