**Data analysis (randomisation to 18 month follow up):** The primary outcome, out-of-home placement, will be described by a Kaplan-Meier graph and summarised by the proportions with out-of-home placement by 18 months. The primary analysis will be Cox regression, adjusting for key predictors which will be pre-specified from a list including centre, site, the minimisation variables, and other risk indicators. We will use interaction tests to explore whether the intervention effect differs according to pre-specified sub-grouping variables (gender, age, presence of criminal record and referral path). Clustering by therapist will be allowed for by computing robust standard errors (but these will be ignored if they turn out to be smaller than conventional standard errors) (Roberts, 1999). Secondary outcomes at each time will be analysed by linear or logistic regression as appropriate. We will also use random effects models to explore differences between randomised groups in trajectories over time. Analyses will be by intention-to-treat: that is, including each individual in their randomised group regardless of the intervention actually received, and performing sensitivity analyses to explore the impact of any missing data.

*Health economics data analysis:* Despite the often skewed nature of costs, mean costs will be compared using standard parametric tests and the robustness of the results confirmed using bootstrapping (Efron & Tibshirani, 1993). The advantage of this approach, as opposed to logarithmic transformation or non-parametric tests, is the ability to make inferences about the arithmetic mean, which is more meaningful from a budgetary perspective (Thompson & Barber, 2000). Details of special school placement will also be recorded as part of the economic data collection. Because schools vary greatly, we generally ask for specific details regarding all non-mainstream schools, including name and address of school so that we can check/verify the type of school, as necessary.

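### The protocol keeps out-of-home placement as the primary outcome but also says some young people who stay at home are coded as failures; the two rules conflict and the stated power fits only the first

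*Protocol*

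**What the plan says.** The Measures section defines the outcome by placement: "The primary outcome will be the proportion of cases assigned to long-term (3 months+) out of home placements in specialist residential provision at 18 months". The section on data analysis from randomisation to 18 months uses the same variable: "The primary outcome, out-of-home placement, will be described by a Kaplan-Meier graph and summarised by the proportions with out-of-home placement by 18 months", with Cox regression as the primary analysis. The Sample size paragraph is also placement-only: 30% against 20%, 350 per arm, 86% power, or 83% after allowing for therapist clustering in the MST arm.

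Participant Adherence gives the reason for the choice: "the primary outcomes consist of data recorded formally (e.g. out of home placements) which can be measured even if participants have dropped out". It expects 5% dropout at each measurement point, 15% in total, and assigns that loss to secondary outcomes. The Measures section adds that placement is the one measure obtainable on everyone, including families lost to interview.

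The Measures section then sets out four combinations of placement and family functioning:

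1. not placed, functioning improved
2. placed, functioning unchanged
3. not placed, functioning still inadequate
4. placed, functioning improved

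It says "while we intend to retain out of home placement as the primary outcome, we intend to interpret the family preservation information" in the light of self-reported wellbeing. The next sentence goes further. It concerns someone who has not been placed but for whom observation at home and self-report point to a poor position. When that "situation is markedly sub-optimal, the outcome would be coded as a treatment failure", and category 2 is given the same code. Category 4 receives no code.

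**The concern.** To say how an outcome is coded is to give a data-handling instruction, and this one stands in the paragraph about the primary outcome. A statistician building the primary variable could follow the definition or the coding sentence and get different event counts.

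If the coding sentence were followed, the main advantage of placement would be lost. The outcome would no longer be complete, because families lost to interview could not be classified. It would no longer rest on formal records. It would also lack an event date for category 3, which the Kaplan-Meier and Cox analyses need. The event-driven interim analysis and the primary economic evaluation both use the primary outcome, so they would inherit the same uncertainty.

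**Working it through.** **Side by side**

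| Feature | Definition, analysis and sample size text | Coding sentence |
|---|---|---|
| Failure if not placed | No | Yes, if the situation is judged markedly poor |
| Failure if placed, functioning unchanged | Yes | Yes |
| Failure if placed, functioning improved | Yes | Not stated |
| Data source | Formal records | Self-report and home observation |
| Expected completeness | Whole sample | About 85% |
| Event date | Date of placement | None for those not placed |

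The Measures section lists interviews, questionnaires and records as its methods. No home observation is among the listed instruments.

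**Reproducing the stated power**

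Inputs from the Sample size paragraph: n = 350 per arm, p1 = 0.30 (control), p2 = 0.20 (MST), ICC 0.02, 30 therapists, design effect 1.22 in the MST arm. Alpha is not stated; I assume 0.05, two-sided.

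Power = Φ[(p1 − p2 − 1.96·SE0)/SE1], where SE0 uses the pooled proportion and SE1 the separate proportions.

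- No clustering: SE0 = 0.03273, SE1 = 0.03251, z = (0.10 − 0.06415)/0.03251 = 1.102, power 86.5%. The protocol says 86%.
- With clustering, the effective MST arm is 350/1.22 = 287: SE0 = 0.03471, SE1 = 0.03403, z = (0.10 − 0.06803)/0.03403 = 0.940, power 82.6%. The protocol says 83%.

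Both figures reproduce, for placement alone.

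**Power if the coding sentence were applied**

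Let q be the share of non-placed young people recoded as failures. Then p1 = 0.30 + 0.70·q(control) and p2 = 0.20 + 0.80·q(MST). The documents give no value for q, so these are scenarios. All placed young people are kept as failures, since category 4 has no code. The last column drops 15% of each arm as unclassifiable (297.5 per arm).

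| q control | q MST | p1 | p2 | Difference (points) | Power, clustered | With 15% missing |
|---|---|---|---|---|---|---|
| 0 | 0 | 0.300 | 0.200 | 10.0 | 82.6% | 76% |
| 5% | 5% | 0.335 | 0.240 | 9.5 | 75% | 68% |
| 10% | 10% | 0.370 | 0.280 | 9.0 | 67% | 60% |
| 20% | 20% | 0.440 | 0.360 | 8.0 | 54% | 47% |
| 30% | 30% | 0.510 | 0.440 | 7.0 | 42% | 37% |
| 20% | 16% | 0.440 | 0.328 | 11.2 | 82.5% | 76% |
| 20% | 10% | 0.440 | 0.280 | 16.0 | 98.8% | 97% |

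If unassessable young people are instead left coded as non-failures, 20% recoding gives p1 = 0.30 + 0.2×0.70×0.85 = 0.419 and p2 = 0.20 + 0.2×0.80×0.85 = 0.336. The standard error is √[(0.419×0.581 + 1.22×0.336×0.664)/350] = 0.0384. Power is then 58% by the unpooled formula, which gives 84% for placement alone.

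**Attrition**

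Suppose MST has no effect, 70% are not placed in each arm, 20% of those are recodable, unassessable cases stay as non-failures, and attrition is 10% in one arm and 20% in the other. The spurious difference is 0.2 × 0.70 × 0.10 = 1.4 points, about 0.4 of the standard error above. The unequal attrition is assumed.

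**The case against.** The strongest reply is that the endpoint has not been changed. The preceding sentence retains placement as primary and gives wellbeing data an interpretive role. The coding sentence follows from that, and it speaks of treatment failure without naming a primary event. The aims, design, sample size, definition and analysis text all use placement, and the 15% attrition is assigned to secondary outcomes. That the Cox model could not use an undated event also favours the interpretive reading. This stands: a reader might infer that the protocol has replaced its record-based endpoint with a judged one, and the text does not support that. What remains is a contradiction that the protocol does not resolve.

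A reader might also infer that the coding rule lowers power. That does not follow. It holds if recoding is equally common in both arms, but the protocol predicts that MST improves family communication and parenting, in which case power could be unchanged or higher. Such a gain would come from family functioning, which is a different question from placement.

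Nor do the documents show that the judgement would be unblinded or that attrition would differ by arm. The Measures section promises blind assessment where possible, and Participant Adherence reports that well over 90% of recruits in either arm of an earlier UK trial were retained for data collection. Both are risks of the rule, not facts about this trial.

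Finally, a cut-off and a rating procedure could properly sit in a statistical analysis plan. Their absence is not the finding; the conflicting rule is.

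**Conclusion.** The concern holds as an unresolved contradiction in the primary outcome. One sentence codes some non-placed young people as failures, while the definition, the analysis, the power basis and the completeness rationale all rest on recorded placement. The stated 86% and 83% are correct for placement alone and cannot be carried over to the coding rule. Under that rule, clustered power runs from about 67% to 42% for equal recoding of 10% to 30%, is about 82.5% at 20% against 16%, and is higher for a wider gap. These figures rest on an assumed two-sided 5% alpha, on recoding rates that the documents do not give, and on keeping every placed young person as a failure. The contradiction itself needs none of these assumptions.

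**What to change.** Take the coding sentence out of the primary outcome text. State that the primary event is recorded long-term placement only, as the Measures section already defines it, and that it counts regardless of family functioning, so that category 4 is settled as well. Keep the four-way classification as a named secondary analysis in participants with questionnaire data, with a cut-off fixed in advance on a listed scale; the 12-item general functioning scale of the McMaster Family Assessment Device is one candidate. Specify blinded rating and the handling of missing questionnaires there. Drop the reference to home observation, or list it as a measure.

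The cost is wording in the protocol and the analysis plan. Sample size and record collection are unchanged, the stated power then applies as written, and the context that the investigators want for interpreting placement is kept.

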#### Design and Methodology (Annual follow up from 2-5 years)

The annual follow-up period from 2 years post randomisation will extend the primary outcome window to 60 months and carry out an evaluation of a broadened range of outcomes of both MST and MAU to 48 months. We will conduct annual full-blind outcome evaluations up to 48 months post-randomisation. Data on service use will be collected using the Child and Adolescent Service Use Schedule (CA-SUS) and Children & Young People, Resources, Evaluation and Systems Schedule (CYPRESS) (Pilling et al., 2012). Data will be used to characterise services and provide currently lacking information on transitions from child to adult services, identifying correlates of a smooth transition (continuation of appropriate services across the 18-year barrier) and testing the hypothesis that transition is important to relatively better outcomes. A a semi-structured interview will explore young people's and primary caregivers' views of change or the absence of change in key outcome domains and the families experiences of services and of the transition between services.

The following domains will be assessed using a comprehensive battery of measures anticipated to take approximately 2-3 hours per assessment (measure in brackets): (i) antisocial behaviour (arrests, reprimands, final warnings or convictions, self-reported delinquency scale, Antisocial Process Screening Device/ICU (Frick & Hare., 2001) (Kimonis, et al., 2008), Achenbach Adult Behaviour Scale (Achenbach, et al., 2013) and emotional well-being and adjustment (Achenbach Youth or Adult Self-Report Scale (YRS)( Achenbach et al., 2013; Achenbach., 1991); Adolescent Resiliency Questionnaire (ARQ) (Gartland et al., 2011); Mental health (services receipt interview, KSADS/SCID (Kaufman et al., 1996; First et all., 1997); (ii) education (school records, interviews, National Pupil Database) and work adjustment ((CLES-A (First et al., 1999), Achenbach Youth or Adult Self-Report Scale(Achenbach et al., 2013; Achenbach., 1991) and the work and relationships information form). (iii) social network (Peer delinguency questionnaire ([name] et al., 2003), Family Adaption and Cohesion scales (Gorall et al., 2006), ARQ (Gartland et al., 2011)) and family outcome (Sib-SDQ (Goodman et al., 1998), Alabama Parenting Questionnaire (Frick., 1991), ARQ (Gartland et al., 2011)), self efficacy (ARQ) (Gartland et al., 2011)) and parenthood (interview); and (iv) physical health (SF-36) (McHorney, Ware., 1995). Diagnostic status will be determined by the K-SADS until participants reach 18 and by the SCID thereafter.

Collecting comorbidity data will inform us of the impact of comorbid disorders on the primary outcome, enabling us to characterise over time the relation between initial trial outcome and subsequent antisocial behaviour, and the presence of these different disorders, and key participant characteristics, e.g. attachment, family relationships and service utilisation. This will have implications for the design of future interventions. Data on MST contacts will be collected directly from the pilot schemes to avoid participants revealing their group allocation to the research assessors. Receipt of all other services is monitored using the Child and Adolescent Service Use Schedule (CA-SUS)

The overall service will be characterised by CYPRESS (Children & Young People, Resources, Evaluation and Systems Schedule) and additional case record extraction measures designed specifically for the trial on the intended and actual MAU as well as the duration and frequency of the intervention. CYPRESS is used to characterise services offering complex interventions for children and young people with conduct disorder and other behavioural problems and check that the necessary elements are in place to deliver the intended objectives of a programme. It aims to understand to what degree particular characteristics are intrinsic to such services, and what relationships exist between particular characteristics and outcomes. This data collection will be carried out annually in person, which will inform us about the extent to which MST services are able to sustain the model and provide information in relation to staff training, employment and turnover, which will be helpful in workforce planning.

Health economic analysis will be continue to be conducted by the Centre for the Economics of Mental Health at the Institute of Psychiatry, London, to explore the relative costs and costeffectiveness of MST and MAU. The evaluation will take a broad perspective, including all health, social services, education and voluntary sector services, plus costs to the criminal justice sector, costs resulting from crimes committed, and out-of-pocket expenses to the young people and families.

**Optional Qualitative Interviews**-The subset of young people and primary caregivers who participate in the qualitative part of the study will receive a semi-structured interview at approximately 42 months (plus or minus 2 months) which will be administered independently. The key domains of the quantitative outcome data will help shape the qualitative semi-structured interview schedule. There will be three primary domains for this enquiry which have been identified because of their putative causal significance in the aetiology of conduct problems: the quality of the parent-adolescent relationship (FACES, ARQ family scale)( Gartland et al.,2011; Gorall et al.,2006), the young person's ability to foster relationships outside the family, including those with non-delinquent peers (SRD, ARQ Peer scale) (Gartland et al.,2011; [name] , McVie.,2003) and perceived ability to meet future challenges (ARQ Self or self-efficacy scale related to confidence (Gartland et al.,2011), social skills and optimism for the future).

The qualitative interviews will focus on the quantitatively assessed central constructs within each of the domains. For example, within the parent-adolescent relationship domain, the constructs of engagement vs. disengagement, high vs. low levels of cohesion and effective vs. ineffective communication will be explored. In relation to the peer domain, interviews will explore the nature of the young person's friendships and the ways in which those who engage with delinquent peers perceive and experience these relationships vs. those who desist from engaging in delinquent peer involvement. In the self-efficacy domain, we will explore the young person's perceived ability vs. perceived inability to meet the developmental challenges of early adulthood such as having supportive relationships and meeting their achievement goals for the future. Finally the interview will also ask questions about the young person's experience of the transition to adult services. While the interview questions will be guided by these constructs they will be transformed into exploratory user-friendly questions.

For example, some sample questions for the third domain are as follows:

1. What do you think it means to become an adult? (prompt: what is the main difference between being a child and being an adult)

2. When you think about your future, what comes to mind? (prompts: time frame, job opportunities).

3. How much control do you think you have over how that future will unfold? (prompt: what abilities do you think you will be drawing on?)

4. Do you think there is help you can draw on to help you as you go through the process of becoming an adult? (prompts: parents, peers, institutions)

While the qualitative arm has clearly been shaped by the quantitative component, it will also have its own integrity. The interviewer will start with the questions on the schedule, but their primary task will be to explore in detail the personal lived experience of the participant within the broad parameters of the domains.

The young people and caregivers will be interviewed separately. They will be interviewed about their experiences of (a) good and bad outcomes across the domains listed above, (b) engagement and contact with services and difficulties encountered, particularly in relation to transition from child to adult services. We will work with MAC-UK young advisors to develop the best format for data acquisition from this group of purposively sampled adolescents. We will also sample 36 clinicians who will be interviewed in the first year of the study in relation to barriers they encountered in implementation and delivery of services. The transcribed interviews will undergo a synthesis of IPA and framework analysis ([name] et all.,2009; Ritchie, Spencer,1994)),

the results of which can then be examined alongside the results of the quantitative analysis of secondary outcome

**Trial management:** There will be 3 Centres: London (UCL and IoP), Leeds and Cambridge. A trial manager at postdoctoral level will be appointed at the UCL site. There will be 4 RAs based at the three research sites (London, with one RA at UCL and one at Iop, Cambridge and Leeds). London will cover 4 MST sites and the others 5 each. They will work semi-independently from others to ensure blindness in coding and interviewing. They will be able to support each other in doing assessments in order to maximise the possibility of blindness (also enforced by instruction to families) so that site A will have an OA from team 1 and someone doing qualitative interview with the same family from Team 2. Economic analysis will be based at the IoP and mediational analysis in Cambridge and the IoP. OAs and the trial co-ordinator will meet weekly across sites by telephone conference. There will be a trial advisory committee including international experts from both Europe and North America.

**Setting up of the Trial Steering Committee (TSC):** In the first phase of the study we will set up a TSC to monitor the progress of the project and advise the research team on matters arising during subsequent phases of the study. The TSC will meet at least quarterly and perhaps more regularly during the preparatory and final stages of the project. The group will be made up of researchers, statisticians, service users and carers, and representatives of professional/ provider organisations, including each link person from the 9 pilot projects. Service users and carers will be drawn from a variety of local groups and national organisations (e.g. Young Minds). The TSC will play a central role in helping us finalise the content of topic guides to be used in the qualitative components of the study. The TSC would also have opportunity to comment upon and inform the final project report. Unwaged service users and carers will receive travel and other expenses and honoraria in accordance with guidance for involving service users.

*Risks and anticipated benefits for trial participants and society, including how benefits justify risks*: There is minimal risk from randomisation and treatment. Both MST and MAU will be delivered by experienced professionals used to working with young people of this age with severe conduct problems. Those who agree to participation in the trial will be involved in a number of time-consuming interviews and assessments (up to 3 hours for baseline assessment, 2 hours for follow up assessments) which may be somewhat burdensome but do not carry specific risk. Given that participant families will agree to provide access to confidential information including the young person's arrest and conviction records, there is potential risk of accidental breakdown of confidentiality which must be met by stringent data-handling safeguards. Benefits to participants will include the provision of intensive high quality care from uniquely trained and supervised clinicians in the MST arm of the trial. Benefits to society will be predominantly through the potential for discovering a clinically and economically effective intervention for a social problem that causes considerable distress not only to the family members involved, but to the social group directly affected by the criminal activities and is a very significant cost to public services as well as the individuals and families concerned.

Informing potential trial participants of possible benefits and known risks: This will be, as outlined above, through the provision of written material as well as discussion with the recruiting MST clinician.

Obtaining informed consent from participants: See above. Informed written consent will be obtained from both the young person who has been referred and at least one parent or carer with legal responsibility.

*Time period for retention of relevant trial documentation:* University College London, as study sponsor, will be responsible for archiving records which will be kept for at least 20 years as per the Research Governance requirements.

*Expected Serious Adverse Event:* Epidemiological data suggest that with a sample of this size it is possible that some young people will be involved in violent crime and inflict or experience

serious injury during the course of the study. In the event of a death associated with the trial, the independent Data Monitoring and Ethics Committee would consider the implications for continuation of the trial. In addition it is possible that families (or indeed coroners) may wish to speak to someone representing the research project about such deaths as well as to local MST staff who have provided treatment. If required the site PIs would be available for such meetings.

Research Governance: UCL has taken on sponsorship and will delegate responsibilities as appropriate to the Principal Investigator, the Centre for Outcomes Research and Effectiveness (CORE), and participating research centres through a Research Sponsorship Agreement. The Trial Management Team housed within CORE will ensure that all approvals (R&D and ethical approvals and other necessary agreements) will be in place at each site through the four participating centres prior to family enrolment. Oversight of the trial will be established in line with MRC GCP guidelines. Oversight will be ensured through the following structure: (a) a core Project Team made up of the PI, trial coordinator and one RA from each Centre, (b) the Trial Management Group (TMG) including the senior co-PIs from each Centre and the trial coordinator , (c) the independent Trial Steering Committee (TSC), and (d) a Data Monitoring and Ethics Committee (DMEC). The TMG will be responsible for the development of trial protocols and their implementation, and will meet at least fortnightly during set-up and monthly or bi-monthly throughout the trial. The function of the TSC will be to provide independent oversight of the trial. It will be chaired independently and will have an independent statistician, independent clinician and service user representation. The TSC will approve the final protocol and meet once during set-up and 6-monthly after recruitment. The DMEC will provide independent review of the safety and ethics of the trial and the interim analysis. The DMEC will comprise an independent statistician and two independent clinicians and will meet once during set-up and annually during the recruitment period. The trial will be conducted to MRC GCP and CORE Standard Operating Procedures which ensure the monitoring and safety of trial participants, internal validity through robust trial conduct and quality assurance systems and high quality reporting to CONSORT standards.

**Data analysis (randomisation to 18 month follow up):** The primary outcome, out-of-home placement, will be described by a Kaplan-Meier graph and summarised by the proportions with out-of-home placement by 18 months. The primary analysis will be Cox regression, adjusting for key predictors which will be pre-specified from a list including centre, site, the minimisation variables, and other risk indicators. We will use interaction tests to explore whether the intervention effect differs according to pre-specified sub-grouping variables (gender, age, presence of criminal record and referral path). Clustering by therapist will be allowed for by computing robust standard errors (but these will be ignored if they turn out to be smaller than conventional standard errors) (Roberts, 1999). Secondary outcomes at each time will be analysed by linear or logistic regression as appropriate. We will also use random effects models to explore differences between randomised groups in trajectories over time. Analyses will be by intention-to-treat: that is, including each individual in their randomised group regardless of the intervention actually received, and performing sensitivity analyses to explore the impact of any missing data.

*Health economics data analysis:* Despite the often skewed nature of costs, mean costs will be compared using standard parametric tests and the robustness of the results confirmed using bootstrapping (Efron & Tibshirani, 1993). The advantage of this approach, as opposed to logarithmic transformation or non-parametric tests, is the ability to make inferences about the arithmetic mean, which is more meaningful from a budgetary perspective (Thompson & Barber, 2000). Details of special school placement will also be recorded as part of the economic data collection. Because schools vary greatly, we generally ask for specific details regarding all non-mainstream schools, including name and address of school so that we can check/verify the type of school, as necessary.

The primary economic evaluation will explore cost-effectiveness in terms of the primary outcome. A secondary cost-utility analysis will be undertaken using Quality Adjusted Life Years (QALYs) calculated using the EQ-5D (EuroQol) measure of health related quality of life (Brooks, 1996; Williams, 1995). Analyses will be undertaken from the societal perspective. Whilst an NHS/Personal Social Services perspective is preferred for submissions to the National Institute of Health and Clinical Excellence, this perspective is likely to be too narrow to capture all relevant costs and effects of this population. However, this narrower perspective will also be reported.

Cost-effectiveness will be explored initially through the calculation of incremental costeffectiveness ratios (ICERs) – the difference in mean costs divided by the difference in mean effects (Van Hout et al, 1994). Repeat re-sampling from the costs and effectiveness data will then be employed to generate a distribution of mean costs and effects for the two treatments (Efron & Tibshirani, 1993), which can be used to calculate the probability that each of the treatments is the optimal choice, subject to a range of possible maximum values (ceiling ratio) that a decisionmaker might be willing to pay for a unit improvement in outcome. Cost-effectiveness acceptability curves will be presented by plotting these probabilities for a range of possible values of the ceiling ratio (Fenwick, Claxton, & Sculpher, 2001). These curves incorporate the uncertainty that exists around the estimates of mean costs and effects as a result of sampling variation and uncertainty regarding the ceiling ratio.

Accurate description of MAU is a key element of the proposed research. Analysis of the service use data collected as part of the economic evaluation will be used to explore patterns of service use and, through multivariate regression analysis, to identify characteristics of young people and their families that are related to total costs. This analysis will help to clarify what MST is being compared to and will help services to better identify and target those young people who are likely to be particularly expensive to support.

